6.2 Assessment of success (Vaccinee questionnaire)

Objectives	Questions	Is the question included in the assessment of success? (Yes/No)	Definition of desirably/correctly answered question	Assessment of success
	Q5. Please select the option that best describes			
	your experience with the Patient information Leaflet for the yellow fever vaccine	Yes	Question completed desirably [1 point 1 or 2 is desirable]	A vaccinee is considered successful for receipt of
Awareness of STAMARIL® PIL (2 questions)	Q6. Please provide any additional comment you may have on the Patient Information Leaflet for the yellow fever vaccine	No	Complementary question	STAMARIL® PIL information when he/she receives the yellow fever pre-vaccination checklist. Success for receipt if ≥80% of vaccinees are successful.

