Furthermore, a patient information leaflet (PIL) should be provided by HCPs to each yellow fever vaccinee which was amended in line with the revisions of the most recent SmPC (dated 15 Feb 2021).

The MAH is also asked to evaluate the effectiveness of implementation of the UK checklist and PIL. Therefore, this post-authorisation safety study (PASS) survey is designed to assess the effectiveness of the UK (STAMARIL®) yellow fever pre-vaccination checklist among the qualified HCPs of designated authorised YFVCs. In addition, this survey will also assess the effectiveness of the the STAMARIL® PIL among yellow fever vaccinees (or their parents/guardians if vaccinees are younger than 18 years old) in the UK.

31-May-2023 Version number: 3.0

Research question and objectives:

The aim of the current study is to examine the effectiveness of the UK (STAMARIL®) yellow fever pre-vaccination checklist among qualified HCPs of designated authorised YFVCs and of the STAMARIL® PIL among yellow fever vaccinees in the UK, by conducting a survey in this population.

The primary objectives of this study are:

1. To measure:

- a. Awareness of the UK (STAMARIL®) yellow fever pre-vaccination checklist by qualified HCPs of designated authorised YFVCs in the UK.
- b. Utilisation of any standardised yellow fever pre-vaccination checklist(s) by qualified HCPs of designated authorised YFVCs in the UK.
- c. Distribution of the STAMARIL® PIL by qualified HCPs of designated authorised YFVCs to yellow fever vaccinees in the UK.
- 2. To evaluate knowledge and understanding of the key safety messages associated with yellow fever vaccination in any standardised yellow fever pre-vaccination checklist(s) among qualified HCPs of designated authorised YFVCs in the UK.
- 3. To verify the receipt of the STAMARIL® PIL by yellow fever vaccinees at the time they get vaccination consultation in the UK.

There is no secondary objective. **Study design:**

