9.7.1 Primary analysis

The general statistical considerations described above will be applied to quantitative and qualitative variables. The number of missing data will be indicated. Missing values are expected to be few and distributed at random. Since there is no applicable method unanimously accepted, there will be no replacement or imputation of missing data.²⁴ Confidence interval of 95% will be evaluated for endpoint variables.

For each question associated with an outcome included in the objectives, a criterion will be applied to separate participants with the correct and desirable answers (or at least one correct and desirable answer as a response if the corresponding question allows multiple answers/true-false or is an open-ended question). These proportions of correct and desirable answers to each question will be expressed for HCPs/vaccinees who answer that question. Analysis for the survey will be performed for HCPs and vaccinees separately for the endpoints described below:

Primary endpoints

- Awareness of the UK (STAMARIL®) yellow fever pre-vaccination checklist will be assessed through the percentage of qualified HCPs who are aware of the checklist.
- Utilisation of any standardised yellow fever pre-vaccination checklist(s) (UK (STAMARIL®) yellow fever pre-vaccination checklist or NaTHNaC/PHS yellow fever pre-vaccination checklist) will be assessed through the percentage of qualified HCPs who frequently or always use any standardised yellow fever pre-vaccination checklist(s).
- **Distribution of the STAMARIL**® **PIL by qualified HCPs to vaccinees** will be assessed through the percentage of qualified HCPs who frequently or always distribute it among yellow fever vaccinees.

- Knowledge and understanding of the key safety messages will be assessed through the percentage of qualified HCPs who provide desirable responses to the related question on key safety messages associated with yellow fever vaccination in any standardised yellow fever pre-vaccination checklist(s).
- Receipt of the STAMARIL® PIL will be assessed through the percentage of vaccinees who receive the PIL.

Secondary endpoint: None Assessment of success

In each survey, the proportion of correct or desirable responses across all questions related to the evaluation of the primary objectives of the surveys will be considered to assess the success.

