best of my knowledge.	Signature of patient	Date (dd/m	ım/
best of my knowledge. Name of patient If applicable	Signature of patient Signature of parent/guardian	Date (dd/m	ım/
Name of patient If applicable Name of parent/guardian	Signature of patient Signature of parent/guardian	Date (dd/m	ım/

Why are these questions important?

How old you are

Babies

There is a greater risk of yellow fever vaccine related brain inflammation (encephalitis)
in very young babies. Babies aged less than six months should not have yellow fever
vaccine and babies aged six to nine months should only be given this vaccine if the
risk of yellow fever at the destination to be visited is high, such as during epidemics/
outbreaks, and travel is unavoidable.

Aged 60 years or older

You are at increased risk of developing serious side effects from the vaccine compared to
younger travellers. If you are travelling to areas where yellow fever vaccine is 'generally
not recommended' you should not receive vaccine. Further information is available in
the NaTHNaC Yellow Fever Information Leaflet for Travellers and on the FitForTravel
Yellow Fever Vaccine page.

How you are feeling today

 Minor illness without high temperature (fever) should not usually delay your yellow fever vaccination. However, vaccination may be postponed until you have fully recovered.
 This is to make sure any symptoms are not confused with possible reactions to the vaccine.

Your allergies and previous reactions to yellow fever vaccine

This vaccine may contain traces of egg, chicken protein and other ingredients that some
people are occasionally allergic to. If you have ever had a serious reaction (anaphylaxis)
to any of the vaccine ingredients, you must tell your health professional; you will not
usually be able to receive yellow fever vaccine.

Your general health and any condition or treatment that may affect your immune system

This vaccine contains live yellow fever virus that has been weakened. Your response to
the vaccine may not be so good if your immune system is weakened by certain illnesses
or treatments, but occasionally the vaccine can still be given. However, if your immune
system is very weak you must not receive yellow fever vaccine as you are at risk of
developing serious side effects from the vaccine, including death.

31-May-2023

Version number: 3.0

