	Q13. Please select the option(s) that best describes the challenges you face while using the yellow fever pre-vaccination checklist (i.e., traveller checklist) issued by the National Travel Health Network and Centre (NaTHNaC) and Public Health	No	Complementary question	

Objectives	Questions	Is the question included in the assessment of success? (Yes/No)	Definition of desirably/correctly answered question	Assessment of success
	Scotland (PHS): Please select all options that apply			
	Q14. Please provide any additional comment you may have on the checklist(s).	No	Complementary question	
Distribution of the	Q15.Please select the option that best describes your experience with the delivery of the STAMARIL® (yellow fever vaccine) Patient Information Leaflet (PIL)	Yes	Question completed desirably [Answers: 1 or 2 are desirable]	An HCP is considered successful for delivery of the STAMARIL®
STAMARIL® PIL (2 questions)	Q16. Please select the option(s) that best describes why you never/rarely/sometimes deliver the STAMARIL® (yellow fever vaccine) Patient Information Leaflet (PIL): Please select all options that apply	No	Complementary question	PIL when he/she always/frequently distributes the STAMARIL® PIL

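### As printed in Annex 6.2, the only scored vaccinee question names neither STAMARIL nor the consultation, and the success rule beside it names the wrong document

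*Protocol*

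**What the plan says.** The third primary objective is "To verify the receipt of the STAMARIL® PIL by yellow fever vaccinees at the time they get vaccination consultation in the UK" (Abstract; also PASS Information and Table 1). It has two qualifiers: the product and the occasion. Table 1 keeps the product in the endpoint but not the occasion. Section 9.7.1 says that receipt "will be assessed through the percentage of vaccinees who receive the PIL", again without the occasion.

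Annex 6.2 lists two vaccinee questions. Q5 concerns "your experience with the Patient information Leaflet for the yellow fever vaccine" and is scored as "Question completed desirably [1 point 1 or 2 is desirable". The other is an unscored free comment: "Q6. Please provide any additional comment you may have on the Patient Information Leaflet for the yellow fever vaccine". The success cell of that row reads "STAMARIL® PIL information when he/she receives the yellow fever pre-vaccination checklist", with a threshold of at least 80% of vaccinees.

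In Annex 6.1 the corresponding HCP question (Q15) asks for the option that best "describes your experience with the delivery of the STAMARIL® (yellow fever vaccine) Patient Information Leaflet (PIL"), so it names the product. Annex 4, the traveller's checklist, sends readers aged 60 or over to "the NaTHNaC Yellow Fever Information Leaflet for Travellers" for further information. Section 9.6.3 and Annex 1 place the full vaccinee questionnaire, dated 31 May 2023, in a stand-alone document.

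**The concern.** With the secondary objective removed, PIL receipt is the only vaccinee endpoint. It rests on one self-reported item, with no question on leaflet content to show which document the respondent has in mind. The respondents are travellers and parents, who may not distinguish a manufacturer's leaflet from other printed yellow fever material. The traveller's checklist itself carries explanatory text on vaccine risk. Someone who did not get the STAMARIL PIL but got something similar could answer Q5 in good faith and be counted as a success.

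That error runs mainly one way. It raises measured receipt and could carry a risk minimisation measure over its 80% threshold when the PIL itself reaches fewer people. The success cell makes this worse: read literally, it scores possession of a different document as receipt of the PIL.

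**Working it through.** **1. Does each statement carry the qualifiers of objective 3?**

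| Place | STAMARIL PIL named? | At the consultation? |
|---|---|---|
| Objective 3 (Abstract, Table 1) | yes | yes |
| Endpoint, Table 1 | yes | no |
| Endpoint, Section 9.7.1 | yes (in its label) | no |
| Q5 stem, Annex 6.2 | no (generic description) | no |
| Success rule, Annex 6.2 | names the checklist as the thing received | no |
| HCP Q15, Annex 6.1 | yes | not applicable |

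The product is lost between the endpoint and the question. The occasion is lost already between the objective and the endpoint. The success rule names a third document. Section 9.2.4.2 shows the same slip: it speaks of vaccinees' answers on their HCPs' use of the checklist, whereas Sections 9.3.2 and 9.4.1 confine the vaccinee questionnaire to PIL receipt, apart from screening and demographics.

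**2. The plan's own figure.** The wording of Q5 has no figure attached. The sample size against which the error would act does: n = P(1−P)·1.96²/e² with P = 0.50 and e = 0.08 (Section 9.5.1) gives 0.25 × 3.8416 / 0.0064 = 150.06, which matches the stated minimum of 150 vaccinees.

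**3. Size of a possible error.** Let r be true receipt of the STAMARIL PIL and f the share of non-receivers who answer desirably because they have another leaflet or checklist in mind. The documents give neither value, so both are assumptions.

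Observed receipt = r + (1 − r)·f

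The f that brings observed receipt to 80% is (0.80 − r)/(1 − r):

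- r = 60%: 0.20/0.40 = 50%
- r = 70%: 0.10/0.30 = 33%
- r = 75%: 0.05/0.25 = 20%

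**4. Chance of meeting the threshold** (at least 120 of 150; exact binomial, responses treated as independent and unweighted):

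| f | r = 70%: observed | chance | r = 75%: observed | chance |
|---|---|---|---|---|
| 0 | 70% | 0.004 | 75% | 0.09 |
| 10% | 73% | 0.03 | 77.5% | 0.27 |
| 20% | 76% | 0.15 | 80% | 0.55 |
| 30% | 79% | 0.43 | 82.5% | 0.82 |

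**5. If receipt is already high.** Section 9.5.1 reports that 90.7% of centres routinely supplied the PIL. That is a figure for centres, not vaccinees. If r were 90.7%, f = 20% would give 0.907 + 0.093 × 0.20 = 92.6%, and the verdict against 80% would not change.

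**The case against.** The strongest reply is that Annex 6.2 is a scoring table and not the questionnaire. The texts of options 1 and 2, and any introduction or product description, are in a document not shown here and may state the product and the occasion. This stands, and it makes the point conditional. It does not remove it, because Annex 6.2 is where the protocol fixes how success is scored, and it prints a stem without either qualifier.

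Second, the sponsor is the only holder of a UK authorisation for yellow fever vaccine, so the phrase in Q5 formally designates one PIL. That also stands. It settles what the phrase means, but not what a lay reader will understand by it. The pilot with 3 non-HCPs (Section 9.4.2) is aimed at such misunderstandings but is too small to exclude them.

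Four stronger readings are tempting and not supported:

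- **Another leaflet counts by rule.** The Q5 scoring does not say so. The risk is respondent error. Only the success cell literally substitutes a document, and that document is the checklist.
- **A leaflet handed over late, or with the survey kit, counts.** The options are unseen, and Section 9.2.4.2 describes the kit as a guide to taking the survey, with no mention of a PIL. Objective 3 speaks of the time of the consultation and draws no line at the injection.
- **Other leaflets are known to be common.** Annex 4 only refers travellers to the NaTHNaC leaflet; nothing says that centres hand it out. The figure of over 90% in Section 7 is centres' use of a traveller checklist and does not estimate f.
- **HCP and vaccinee PIL results would be wrongly compared.** Section 9.7 presents them separately and plans no such comparison.

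**Conclusion.** The point holds in a limited form. The printed stem of the sole scored vaccinee item omits both qualifiers of objective 3, and the success rule beside it names the checklist in place of the PIL. The second is a plain contradiction with objective 3 and Table 1, whatever the answer options say. The first is a measurement risk that depends on those options. If they do not supply the product and the occasion, misreporting of which document was received biases the receipt indicator upward.

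The size cannot be determined from the documents. Under assumed values, a false success needs either sizeable misreporting (33% of non-receivers at true receipt of 70%) or true receipt already close to the threshold (20% at 75%). If receipt among vaccinees is near the 90.7% reported for centres, the conclusion against 80% would not change.

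**What to change.** In the vaccinee questionnaire and in Annex 6.2:

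- Reword Q5 to ask whether the STAMARIL (manufacturer's) patient information leaflet was received at the vaccination consultation visit.
- Add an answer option for a different yellow fever leaflet or checklist, scored as not received.
- Change the success rule to receipt of the STAMARIL PIL, and carry the consultation timing into the endpoint wording in Table 1 and Section 9.7.1.
- If the stand-alone questionnaire already states product and occasion in its options, copy those texts into Annex 6.2. The stem then needs no rewording, but the success rule still does.

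A picture of the leaflet's front page would help but is optional.

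The cost is small, because the questionnaire is being re-issued with this amendment. Completions under the current wording (9 as of 24 May 2023, plus any before the change takes effect) must be flagged or reported separately. Measured receipt may come out slightly lower.
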